**Encrypted email to prescribing clinician:**

Dear [name],

One of your patients, XXX, may be eligible to participate in a study titled “Assisting Veterans in the Safe Use of Prescription Opioids.” Please see their information below.

Name: <<Last>>, <<First>>, <<Middle>>  
Last 4: <<Last4>>

Our recruitment entails sending Mr./[name] a letter and then following up with him/her via phone one week later.

If you have any questions or concerns please do not hesitate to contact the study's principal investigator, [name] at [[contact]](mailto:[contact])

Thank you,

[name]

**Referrals from BHL**

In addition, we will take referrals from BHL. BHL will refer subjects based on any alcohol and/or use of opioid. If a Veteran expresses interest in our study to a member of the BHL team, study staff will be notified and will call the Veteran to further explain the study and perform a screening (phone script provided).

In this scenario, there are a few potential outcomes of the screening call:

- If referred from the BHL and eligible: Results of screening call and patients' decision to participate will be communicated to the BHL. A counselor from the study team will perform the Brief Intervention. If participant decides not to participate, services at the CMCVAMC will continue as if participant had never been referred to the study. A research note describing the outcome of screening call will be created in CPRS.
- If referred from the BHL and ineligible: Results of screening call and ineligibility to participate will be communicated to the BHL. Services at the CMCVAMC will continue as if participant had never been referred to the

study. A research note describing the outcome of screening call will be created in CPRS.

We will ask potential participants if they have texting capability during the initial phone screen. Cost of using the phone for texting and receiving calls will be covered by the participant but minimized as much as possible. In previous work, we found that only 2 of the 125 individuals screened for a study of treatment for substance abuse did not have a mobile phone and all participants' phones were SMS ready with 60% of participants having unlimited messaging plans.

For those who are potentially eligible following the phone screen (and interested in participating), the next step is coming to the VA for consent. After consent, subjects will complete the first research visit. Final eligibility is determined after consent using the SCID and MINI. If after learning more about the study during the consenting process, the Veteran decides not to consent, or if they are ineligible following the SCID and MINI, then the Veteran will continue to receive services at the CMCVAMC to which they are eligible and entitled to. This could include services through the BHL or MHC. Similarly, Veterans can also elect to stop their participation in the study and can withdraw without penalty in writing using the revocation form at any time after they have consented to the study. In this case, their normal care at the CMCVAMC will continue.

Veterans who meet criteria for participation will be randomly assigned to either receive the usual care (that which they would have gotten if they had not chosen to be in the study); or Prevention Intervention (PI).

As a result of relaxing our inclusion criteria, it is likely that we will randomize Veterans who have not consumed alcohol in the past three months. For those Veterans, we will monitor their alcohol use during the research follow up visits at 3, 6, and 9 months. If they report having a drink of alcohol, we will then begin which treatment arm they had been randomized to. If the Veteran does not report taking a drink prior to the 9 month follow up, they will simply continue with the 12 and 18 month follow ups but will never have the Brief Intervention or Prevention Intervention.

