e. **Summary of Findings from Our Research Program.** These studies demonstrate our ability to recruit large samples in a timely fashion, enroll Veterans who are engaging in risky drinking into research studies, deliver interventions over the telephone, and maintain high follow-up rates across periods as long as 24 months. Three of these studies also provide evidence to support the effectiveness of enhanced or extended interventions for patients who do not evidence a good initial response to alcohol/drug treatment.

I. **Purpose of the Project:** (Clearly provide the purpose of this research project.) In this application, we propose to test an integrated prevention intervention, designed to reduce rates of risky drinking in Veterans receiving prescription opioids for chronic pain management or opioid replacement therapy. For Veterans on opioid replacement therapy, they must have a chronic pain diagnosis. This adaptive, patient-centered intervention provides integrated clinical assessment, brief intervention, monitoring, and extended prevention services delivered through a combination of telephone calls, and text messages.

J. **Describe the Research Questions or Hypotheses** (that is, what questions are you trying to address by conducting the research.)

1. **Primary objective:** To compare the effectiveness of a 12-month prevention intervention (PI) with a brief intervention only group (BIO) over an 18-month follow-up period, for Veterans treated with prescription opioids and who are engaging in risky/hazardous drinking, based on NIAAA guidelines.
  - *Hypothesis 1:* PI will produce better outcomes than BIO, as indicated by lower rates of risky/hazardous alcohol use across the follow-up period.
2. **Secondary objectives:** To examine secondary outcome measures, moderator effects, and mediation effects:
  - *Hypothesis 1:* PI will produce better outcomes than BIO on frequency of heavy drinking, biological measures of heavy drinking (i.e., GGT and CDT), urine toxicology tests to assess other drug use, depression, and pain.
  - *Hypothesis 2:* Rates of opioid overdoses will be lower in PI than in BIO
  - *Hypothesis 3:* Intervention effects will be greater in higher-risk Veterans, including those with higher prescription opioid dosages, co-occurring benzodiazepine use, poor social support, and low readiness for change.

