- 2.2. Describe how randomization or other treatment assignment will be made. **Veterans who meet criteria for participation will be randomly assigned to one of the two treatment conditions. Urn randomization will be used to balance the groups on three factors: gender, benzodiazepine or other drug use, and age. We will also be blocking on whether the person admits use or not when we do the randomization, so we get equal numbers of non-users in each condition. Urn randomization is a kind of biased-coin randomization where probability of being assigned to a group decreases if the group is overrepresented and increases if the group is underrepresented. As the sample size increases, the randomization shifts from perfect balance to complete randomization.**
- 2.3. For retrospective research studies, provide the "look-back" period. (e.g., December 1, 1999 through December 31, 2008.) **n/a**

3. **Study Duration**

- 3.1. Provide the estimated length of time to enroll all subjects and complete the study. **2.5 years of enrollment, but 5 years total for study start up, enrollment, completion, and analyses.**
- 3.2. Explain the expected duration of subject participation including any follow-up. **18 months for patients enrolled prior to 4/1/2019; 12 months for patients enrolled after 4/1/2019**
- 3.3. Specify the projected date of completion of the proposed study. **5 years from date of funding.**

4. **Drug Information** (If not applicable state, "Not Applicable.") **Not Applicable**

- 4.1. Specify if the drug or biological agent is:
  - 4.1.1. FDA approved
  - 4.1.2. Used for off-label purposes
  - 4.1.3. Not yet FDA approved.
- 4.2. Include the FDA Investigational New Drug (IND) number for all non-FDA approved and off-label drugs, biological agents or nutritional supplements. If not applicable state, "Not Applicable."
- 4.3. Provide all relevant information about the drug
- 4.4. Explain any wash-out periods, rescue medications permitted and any type of medications not permitted while enrolled in the study.
- 4.5. Describe blinding and un-blinding procedures.

- 4.6. Include the dosage, route of administration, previous use, and the safety and efficacy information on any drug used for research purposes.
- 4.7. Describe rationale for the dosage in this study.
- 4.8. Justify why the risks are reasonable in relation to anticipated benefits and/or knowledge.
- 4.9. Describe where drug preparation will be done.

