As part of broadening the inclusion criteria we plan to add a third group to the adaptive intervention. We will enroll and randomize the Veterans who do not admit to drinking and place them in a monitoring category where we continue to assess them and if they admit to consuming any amount of alcohol we would then transfer them to the treatment arm into which they had been randomized. This change is a significant change to the study but does not change the aims or outcomes and it does not increase the risk. It is a change supported by the DOD as a way to increase enrollment and reach veterans that we think may be less truthful about their alcohol use out of fear that they will have their opiate prescriptions taken away.

Following up those who initially deny drinking will provide important data for the VA. The yearly AUDIT screening appears to be underestimating the numbers of vets who are drinking alcohol. If our data indicate that a significant percentage of those who deny drinking at the start of the study end up reporting drinking later in the follow-up, it will be in indication that at risk patients (i.e., those on opioid meds) are at risk due to underreporting of their drinking, which could be an unintended consequence of the current VA policies.

We also will no longer be using the AUDIT-C.

Additionally, we have decreased the total n for the study to 150 from all sites. That is, 200 subjects from all sites being randomized (with 150 participants drinking and entering TX phase and 50 participants not drinking (25 at CMCVAMC and 25 at Penn).

Moreover, there is a personnel change. [name] is no longer a Research Coordinator on this study.

Lastly, SenseHealth has changed its name to Wellpass and the TRC has moved its location to [name]

At the time of this amendment, the following number of subjects have been randomized at the following sites:

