The primary outcome measure will be rates of risky drinking (i.e., more than 4 drinks at any one sitting or more than 14 drinks/week for men; more than 2 drinks at any one sitting or more than 7 drinks/week for women) within each follow-up period (e.g., months 1-3, 4-6, 7-9, 10-12, 13-18), as determine by the TLFB. Secondary outcomes in the study will be self-reported frequency of heavy drinking days (TLFB), biological measures of alcohol use (%dCDT and GGT), urine toxicology tests to assess other drug use, VA medical records of opioid overdoses, depression, and pain. Outcome data will be analyzed using mixed effect regressions for continuous and categorical data (i.e., SAS) and various packages to examine mediation effects (i.e., MPlus). The alpha level for the primary outcome will be set at 5%.

Data quality will be monitored by random inspection of the completed forms by the research coordinator and any problems detected will be discussed with the PI. The Research prevention counselors will receive standardized training on the interventions, which are all manualized. Adherence to the manuals will be monitored using audiotapes and individual supervision provided by the clinical coordinator. If drift is observed the counselors will be re-trained.

Blind interim analyses of the data will be conducted at two points when 50 and 75% of the sample has been accrued. If the results show statistically overwhelming significant differences between groups, the study will be stopped (or one of the conditions stopped).

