3. If applicable, define the plan for subjects if research shows results such as:

- 3.1. Depression If depression appears to be an issue for a participant, and they are not already receiving treatment, the research staff will consult with [name] for a consult with the participant and a possible referral.
- 3.2. Suicide Participants who indicate any suicidal ideation will be evaluated by [name], [name], or [name] at the CMCVAMC.
- 3.3. Abuse It is anticipated that the Veterans in our study will be engaging in alcohol or drug abuse. [name] will be consulted in the event there is significant change to the Veterans' use status. If the Veteran is in danger in terms of physical abuse or someone else is in danger due to the Veteran abusing them, [name] will be consulted and the appropriate actions will be taken.

4. Statistical Analysis

- 4.1. Include statistical power calculations and the assumptions made in making these calculations. **We consider the primary hypothesis of risky alcohol use, which compares PI and BIO groups on five repeated binary outcomes. We use the sample size formulae of Diggle et al. We expect to have a 20% dropout rate by month 18, and to see a risky drinking rate of 30%. On the assumption of a within subject correlation of 0.3 (resp. 0.4, 0.5), our sample size of 150 per group provides 80% power for a main effect difference of 30% versus 20% (resp. 30% versus 19%, 30% versus 18%) for the BIO versus PI groups.**

**March 2018 Amendment:** Our original power analysis in the grant was very conservative, as it took into account multiple outcome measures and moderation and mediation analyses. We had our statistician re-run the analyses, focusing on the main effect treatment group comparison with the primary outcome measure. If we calculate sample size needed to have 80% power to find a 15- percentage point difference in rates of risky drinking between the two conditions (e.g., 35% control condition vs. 20% experimental condition on risky drinking rate), we need a total of 136 to 162 veterans (depending on different estimates of the correlation between the outcome measure at different follow-up points). If the effect is slightly larger (e.g., 20 percentage point difference), we only need 72 to 84 veterans in total. Therefore, with a combination of the new design we are confident that we will reach a sample size that will be sufficient to at least examine our primary outcome measure.

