- 4.2. Define plans for data and statistical analysis, including key elements of the statistical plan, stopping rules and endpoints.
  - a. Primary objective: The responses for the primary hypothesis comprise five repeated binary measurements per participant indicating risky alcohol use over the follow-up points. Our main analyses will use mixed effects logistic regression models to compare the two groups on the rates of risky alcohol use. We expect that linear and quadratic trends will account for the patterns of use across time. If residual analyses suggest significant lack of fit, we will examine more general time trends using spline specifications. The main explanatory variable will be a binary factor indicating intervention group, together with terms for time trends, and for group by time interactions, if appropriate. Based on analyses of similar data, we expect that a random intercept model, possibly with an autoregressive repeated measures structure, should provide a good fit to the covariance structure of the repeated measures, although we will examine more general specifications, if necessary. The estimated regression coefficients for the group variable, and possibly for group by time interactions, will address our primary hypothesis. We will test whether estimated coefficients are different from zero, and will report estimates and approximate 95% confidence intervals.

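### Baseline non-drinkers are randomised but untreated unless they later report a drink, and the plan does not say whether or from when they count in the primary analysis

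*Combined protocol and SAP*

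**What the plan says.** - **Who is randomised.** After the inclusion criteria were relaxed, section O.1 expects that "it is likely that we will randomize Veterans who have not consumed alcohol in the past three months". Their drinking is checked at the 3-, 6- and 9-month visits. A reported drink starts the assigned arm; without one they stay in follow-up and never receive the Brief Intervention (BI) or the Prevention Intervention (PI). The March 2018 amendment in O.1 describes the same step: on admitting any alcohol, staff would "transfer them to the treatment arm into which they had been randomized". It counts 200 randomised, 150 drinking and 50 not.
- **Whom the objective concerns.** Section J.1 compares a 12-month PI with BI only in Veterans "who are engaging in risky/hazardous drinking, based on NIAAA guidelines".
- **The clock.** Study visits (O.1) are timed from baseline for everyone. The outcome windows in W.1 run from months 1-3 to months 13-18. Section M.3.2 sets participation at "18 months for patients enrolled prior to 4/1/2019; 12 months for patients enrolled after 4/1/2019".
- **The analysis.** W.4.2a fits a mixed-effects logistic model to five repeated binary measures, with intervention group as the main explanatory variable: "We will test whether estimated coefficients are different from zero". No section defines a primary analysis set, excludes non-drinkers or moves time zero to the start of treatment.
- **The stratum.** M.2.2 blocks the randomisation on whether the Veteran admits use.
- **Power.** W.4.1, as amended in March 2018, claims "80% power to find a 15- percentage point difference in rates of risky drinking between the two conditions", for example "35% control condition vs. 20% experimental condition on risky drinking rate", with 136 to 162 Veterans in total.

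**The concern.** Until the trigger the two arms are identical for these Veterans, so their untreated windows cannot show an effect of PI. Pooled as randomised, those windows pull the estimate towards zero by an amount that depends on how many Veterans happen to report a drink and when. The result would then answer a different question from J.1, and the sample-size statement, which assumes an undiluted 35% versus 20%, would not apply to it.

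Follow-up is also cut short. A 12-month PI started at month 9 would run to month 21, past the 18-month visit. On the 12-month schedule any start at month 3 or later outruns the last visit.

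Finally, the trigger is a self-report made after allocation exists, by Veterans who the March 2018 amendment suspects may under-report. Allocating early buys nothing in return, because the stated wish to learn how many deniers later report drinking can be met by following them unassigned.

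**Working it through.** **Inputs.** Rates of 35% and 20%, and 80% power (W.4.1). Alpha 5% (W.1), taken as two-sided because W.4.2a tests for any difference from zero. Five measures per participant (W.4.2a). 200 randomised, 50 of them non-drinkers (March 2018 amendment); the other 150 are assumed to be drinking at baseline. Equal allocation. The amendment does not give its correlations, so 0.3, 0.4 and 0.5 are taken from the pre-amendment calculation in W.4.1. It states no dropout either; about 10% average loss is assumed, against the 20% by month 18 in the pre-amendment text.

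**Step 1: the plan's own figure.** For two proportions with mean p̄ and difference d, n per arm = [1.96·√(2p̄(1−p̄)) + 0.8416·√(p₁(1−p₁) + p₂(1−p₂))]² / d².
- For 35% versus 20%, p̄ = 0.275 and n = (1.238 + 0.524)² / 0.0225 = 137.9.
- Multiply by (1 + 4ρ)/5 for five correlated measures: 137.9 × 0.44 = 60.7 at ρ = 0.3, and 137.9 × 0.52 = 71.7 at ρ = 0.4.
- Double for the total (121.4 and 143.4) and divide by 0.90: **134.8 and 159.4**, against the stated 136 and 162.
- The same steps for 35% versus 15% give 70.8 and 83.7, against the stated 72 and 84.

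The figures therefore reproduce under these assumptions, and they describe a population in which everyone can respond to treatment.

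**Step 2: size of the dilution.** On the five-window schedule, 200 Veterans give 200 × 5 = 1000 person-windows. Assume a 15-point effect in treated windows and none in untreated windows.

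| All 50 non-drinkers start at | Untreated windows | Average difference |
|---|---|---|
| month 3 | 50 × 1 = 50 (5%) | 15 × 0.95 = **14.25** points |
| month 6 | 50 × 2 = 100 (10%) | 15 × 0.90 = 13.5 points |
| month 9 | 50 × 3 = 150 (15%) | 15 × 0.85 = 12.75 points |
| never | 50 × 5 = 250 (25%) | 15 × 0.75 = **11.25** points |

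If none starts and none drinks at risky levels, the rates are 0.75 × 35% = 26.25% and 0.75 × 20% = 15%, which again differ by 11.25 points. On the four-window (12-month) schedule the untreated share runs from 50/800 = 6.25% to 25%, so the average runs from 14.06 to 11.25 points.

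**Step 3: power in the last case.** Beta-binomial simulation with 20,000 runs, five windows and no dropout. Participant means are compared by t test, or by linear regression on arm and stratum. Each arm has 75 drinkers, with or without 25 Veterans at zero.

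| Analysis | ρ = 0.3 | ρ = 0.4 | ρ = 0.5 |
|---|---|---|---|
| 150 drinkers only | 87% | 81% | 76% |
| All 200, unadjusted | 83% | 76% | 72% |
| All 200, adjusted for admitted use | 87% | 81% | 76% |

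The closed formula gives 87.7, 81.7 and 76.0% for the 150 drinkers without loss, and 84.0, 77.6 and 71.5% with 10% loss. Adjustment restores the power because it removes the variance between strata, but the estimated difference stays at 11.25 points.

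**Step 4: counts that do not agree.** Section R.1 targets 115 + 60 = 175, not 200. If 50 of the 175 are non-drinkers, 125 drinkers remain, and power without loss is 81.2, 74.3 and 68.1%. The gap may instead be Penn's 25 non-drinkers, since 90 + 10 + 50 = 150 and 150 + 25 + 25 = 200. The documents do not settle this.

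**The case against.** The best defence is that the documents never place the 50 in the primary model, and several passages point the other way. J.1 is about risky drinkers. The amendment counts 150 drinking Veterans apart from 50 others. R.1 describes 25 at the coordinating site as followed only. The 136 to 162 requirement brackets 150. Blocking on admitted use makes the drinkers a balanced stratum fixed before allocation. All of this stands. It shows that a restricted analysis would be sound and may have been intended, but W.4.2a does not state it. Blocking balances the arms; it does not define an analysis set or time zero.

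Three stronger readings are tempting and are not supported.
- **That the trial will lose 3.75 points of effect.** 11.25 points is the worst case. The amendment enrols these Veterans because some may prove to be drinking, and early starts bring the figure close to 15.
- **That power is necessarily damaged.** The loss belongs to an unadjusted pooled comparison; including the existing blocking factor removes it.
- **That disclosure will differ by arm.** Double-blind is unchecked in M.2.1, but no passage says untriggered Veterans know their arm. This is a risk only.

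The month-9 example also rests on one reading of O.1. It lists the 9-month visit among the checks, but describes never-treated Veterans as those reporting no drink before that visit.

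**Conclusion.** The point holds as a gap in the plan: the primary analysis set and time zero are undefined for a quarter of those to be randomised. Read literally, W.4.2a pools them. The expected difference then falls from 15 points to between 14.25 and 11.25 on the five-window schedule (14.06 to 11.25 on the four-window schedule). At the lower end an unadjusted test loses about 5 points of power at each correlation. The main harm is to interpretation, because the estimate would depend on how many non-drinkers trigger and when.

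These figures assume 150 baseline drinkers plus 50 others, a 15-point effect in every treated window, no difference in untreated windows and, for power, no dropout. The conclusion does not depend on disclosure differing by arm.

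**What to change.** 1. **Primary analysis set.** Define it before analysis as Veterans drinking at baseline, the pre-randomisation stratum in M.2.2, with time zero at randomisation. If all randomised Veterans are also analysed, include that stratum in the model and label the result a sensitivity analysis. Cost: a few lines of text. Power stays at 87/81/76% without dropout if 150 drinkers are enrolled.
2. **Non-drinkers already randomised.** Report them separately. Label any analysis counted from the trigger visit as secondary and exploratory, because it selects on a self-report made after randomisation.
3. **Non-drinkers still to be enrolled.** Follow them unassigned and randomise at the visit where a drink is first reported, with windows counted from that date. Cost: an amendment, a randomisation step at a scheduled visit and a smaller randomised total. Follow-up after a late trigger is cut short by the existing last visit (month 12 or 18) unless visits are added.
4. **Passages to reconcile.** O.1 limits the trigger to about month 9, while R.2.1.1 sets no limit. The Brief Intervention text in O.1 says both groups receive or are scheduled for BI, while an earlier paragraph of O.1 says some never will. The March 2018 amendment gives 200 randomised, while R.1 sums to 175.
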